9.3.4.2 Clinical laboratory evaluations

For continuous laboratory data: values of the form “ $< x$ ” (i.e., below the limit of quantification) will be imputed as x divided by 2 in the computation of descriptive statistics. Laboratory values that are recorded in the form “ $> x$ ” (i.e., above the limit of quantification) will be imputed as x in the computation of descriptive statistics. Raw formats will be presented in listings.

Urinary glucose will be treated as continuous, with the value ‘Negative’ imputed as 0.

9.3.4.3 Vital signs

No derivations are required for absolute values of vital sign endpoints.

9.3.4.4 Electrocardiogram (ECG)

Where three screening measurements of QtCF are carried out (in the case that QtCF is >450 for males or >470 for females), QtCF at screening will be the average of the three assessments. No further derivations are required for ECG endpoints.

9.4 CLINICAL PHARMACOLOGY

9.4.1 Pharmacokinetics

Concentrations that are below the limit of quantitation (BLQ) will be derived as the lower limit of quantification (LLOQ) value divided by 2 in the computation of descriptive statistics.

9.5 ASSESSMENT TIME WINDOWS

9.5.1 Definition of permissible time windows

All study visits from baseline to Week 48 have a window of +/- 7 days inclusive in the schedule of assessments. For the purpose of efficacy, PK and safety analysis, visit windows will be treated as continuous, from the midpoint between two consecutive study visits:

Visit	Window
Screening	From enrollment to randomization

REACH TRIAL

Baseline	Day of randomization, or date of last non-missing value obtained prior to the first dose of study treatment.
Week 4	Days 15 to 56
Week 12	Days 57 to 126
Week 24	Days 127 to 210
Week 36	Days 211 to 294
Week 48	Days 295 to the earliest of Day 357 or Day of OLE Study Drug Dose 1

Data collected after the first dose of study treatment up to and including Day 14 will be treated as unscheduled. Where there is more than one measurement within a visit window, the visit closest to the target visit date will be included for analysis. Where two visits are equidistant to the target visit date, the later visit will be included for analysis. Data collected during visits that are excluded because another is closer to the target visit date will be treated as out-of-window observations.

Efficacy and PK data from both scheduled and unscheduled visits and from Early Termination visit will go through the above windowing process. Similarly, safety data from scheduled visits, from Early Termination visit and from Safety Follow-up visit will go through the above windowing process.

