9.3.1.4 On-treatment

For patients that do not prematurely discontinue treatment, all post-baseline measurements on or before the end of the Week 48 window are considered on-treatment.

For patients that do prematurely discontinue treatment, only measurements that are taken whilst a patient is taking the study treatment will be on-treatment measurements. More specifically if:

$$(\text{Assessment date}) - (\text{Date of first dose}) + 1 > 0; \text{ and} \\ (\text{Date of last dose}) + 2 - (\text{Assessment date}) \geq 0$$

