10.3.5 Clinical laboratory evaluations

Laboratory data (hematology, biochemistry, and urinalysis) will be presented as follows:

For each timepoint (baseline, weeks 4, 12, 24, 36 and 48, and the safety follow-up visit) absolute values and change from baseline will be summarized with standard summary statistics (see Section 8.1), by treatment group.

For the following hematology (hemoglobin, red blood cell count, hematocrit, total white blood cell count, # lymphocytes, neutrophils, basophils, eosinophils, and platelet count), biochemistry (total bilirubin, alkaline phosphatase, aspartate aminotransferase, alanine aminotransferase, gamma-glutamyltransferase), and urinalysis (glucose, blood and protein) parameters: shift from baseline will be tabulated for all patients with a baseline value as well as at least one post-baseline measurement, by treatment group: the number and percentage of patients at baseline classified as low, normal or high and overall will be presented; and the shift from baseline category to (a) lowest post-baseline category; and (b) highest post-baseline category. For parameters which have classifications in both the high and low direction, these will be summarized separately.

Hematology, biochemistry and urinalysis data will be presented in separate listings, by treatment group and FSHD type. Each listing will present patients' data by visit. Patients' 3 highest and 3 lowest results outside of the normal range for each variable will be flagged in the listings. Data from unscheduled visits and any early termination (ET) visit will be included in this assessment of low and high results.

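### Safety follow-up data are windowed into treatment visits, so an off-drug value can stand as the Week 48 safety result and be labelled on-treatment

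*SAP*

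**What the plan says.** SAP 9.5.1 builds the analysis windows so that "visit windows will be treated as continuous, from the midpoint between two consecutive study visits". The last row of the table, Week 48, covers "Days 295 to the earliest of Day 357 or Day of OLE Study Drug Dose 1". No row exists for the follow-up visit. On which data enter, the section says that "safety data from scheduled visits, from Early Termination visit and from Safety Follow-up visit will go through the above windowing process"; the matching sentence for efficacy and PK data does not name the follow-up visit.

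Two selection rules apply: "Where there is more than one measurement within a visit window, the visit closest to the target visit date will be included for analysis", and "Where two visits are equidistant to the target visit date, the later visit will be included for analysis". The visit that loses becomes out-of-window. Under SAP 9.5.2 it is then unscheduled and leaves the by-visit summaries, but stays in listings and in the search for minimum, maximum and worst results.

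SAP 10.3.5 plans laboratory summaries as follows: "For each timepoint (baseline, weeks 4, 12, 24, 36 and 48, and the safety follow-up visit". SAP 10.3.6 does the same for vital signs. Both treat follow-up as a separate row.

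For patients who do not stop treatment early, SAP 9.3.1.4 says that "all post-baseline measurements on or before the end of the Week 48 window are considered on-treatment", without reference to the date of last dose. For those who do stop early, the limit is last dose plus 2 days.

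**The concern.** The follow-up visit exists to observe patients off drug. Under 9.5.1 its values compete with the on-drug Week 48 values for one slot, and the date alone decides. The separate row required by 10.3.5 and 10.3.6 cannot be filled properly from the same text. A follow-up value inside the windows is either used as a treatment visit or set aside as unscheduled, so a programmer has to disregard one section.

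At stake is the meaning of the by-visit laboratory and vital-sign summaries, of the by-visit liver-test counts in 10.3.4, and of the on-treatment categories for QTcF, vital signs and weight in 10.3.6 and 10.3.7. Protocol 1.3.2.1 reports that ALT elevations generally reversed after the drug was stopped, so on-drug and off-drug values are not interchangeable.

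**Working it through.** **1. Reproduce the windows.** The nominal days are 1, 28, 84, 168, 252 and 336. Successive midpoints are 14.5, 56, 126, 210 and 294, which give every boundary in the table up to the start of Week 48. The upper limit, Day 357, is 336 + 21. It is not a midpoint with either follow-up contact: (336 + 343)/2 = 339.5 and (336 + 373)/2 = 354.5. Nothing therefore separates Week 48 from follow-up.

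**2. Inputs.**
- Week 48 visit: Day 336 ± 7, that is Days 329 to 343 ("All study visits from baseline to Week 48 have a window of +/- 7 days inclusive in the schedule of assessments").
- Follow-up visit: 7 days after last dose. The interval is blacked out in the protocol; 7 comes from SAP 9.3.4.1 and from study days 336 and 343 in the schedule. The visit window is ± 3 days.
- Last dose on the Week 48 visit day. This is an assumption, supported by in-clinic dosing with pre-dose and 4-hour PK samples at Week 48 (SAP 10.5.1.1 and Appendix B).
- Patients with a Part A follow-up visit: early discontinuers and completers who do not roll over (Protocol 3.1.1).

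**3. When follow-up replaces Week 48.** Let v be the Week 48 day minus 336 (−7 to 7) and k the gap to follow-up. Follow-up is chosen when |v + k| ≤ |v|, that is when v ≤ −k/2.

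For k = 7 this gives v ≤ −3.5, or Days 329 to 332. For example, with Week 48 on Day 330 (6 days from target) and follow-up on Day 337 (1 day from target), the off-drug value is kept. On the nominal 336/343 schedule the distances are 0 and 7, and Week 48 is kept.

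Over all permitted gaps:

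| k (days) | 4 | 5 | 6 | 7 | 8 | 9 | 10 | Total |
|---|---|---|---|---|---|---|---|---|
| Week 48 days displaced, of 15 | 6 | 5 | 5 | 4 | 4 | 3 | 3 | 30 of 105 |

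The displaced Week 48 visits lie on Days 329 to 334.

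**4. Calendar reading.** If follow-up is instead read as Day 343 ± 3 (Days 340 to 346) and must come after Week 48, there are 95 pairs. Replacement occurs with Week 48 on Days 329, 330, 331 and 332, in 4 + 3 + 2 + 1 = 10 of them.

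**5. Early discontinuers.** With last dose and an assessment on Day 160 and follow-up on Day 167, the distances from the Week 24 target (Day 168) are 8 and 1. The follow-up value becomes the Week 24 result.

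**6. On-treatment label.** For a non-rollover completer, follow-up falls between Day 329 + 4 = 333 and Day 343 + 10 = 353, always on or before Day 357. All 105 pairs are labelled on-treatment at 4 to 10 days off drug. For an early discontinuer, (last dose + 2) − (last dose + 7) = −5, which is below 0, so the 7-day follow-up value is not on-treatment.

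**The case against.** The strongest reply is that little safety signal can be lost.
- A displaced Week 48 value still counts in the minimum, maximum and worst results (SAP 9.5.2, 10.3).
- Laboratory shift tables use the lowest and highest post-baseline category, not the on-treatment label (10.3.5).
- Adverse events of special interest are derived from liver tests without a visit restriction (9.3.4.1).
- The affected group is limited. Completers who roll over have no Part A follow-up visit, and their window closes at the first open-label dose.
- By-visit summaries contain some off-drug values anyway, because patients who stop treatment are encouraged to keep attending scheduled visits.

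All of this stands. It confines the consequence to by-visit descriptives, by-visit liver counts and the on-treatment categories. It does not remove the conflict between sections.

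A reader might infer more than the documents support:
- **That about 29% of patients are affected.** 30/105 is a share of permitted day pairs. The documents give neither the distribution of visit days nor the number of non-rollover completers.
- **That QTcF effects are diluted.** Adding a value cannot lower a maximum, and the completer's Week 48 value also stays on-treatment. The category can only stay the same or become more extreme.
- **That a creatinine or ALT signal is hidden.** Protocol 1.3.5.1 says the creatinine rise also attenuated with continued therapy, and the ALT events in the FSHD studies resolved with continued dosing. How far a Week 48 mean would move is not known.
- **That the follow-up row will be empty or duplicated.** The table shells are a separate file that was not available here. The text shows only that the row cannot be filled consistently.

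**Conclusion.** SAP 9.5.1 conflicts with 10.3.5 and 10.3.6. Followed as written, it can put an off-drug value in a treatment-visit row. For non-rollover completers this needs an early Week 48 visit: Days 329 to 332 for an exact 7-day gap, 30 of 105 day pairs with 7 ± 3 days, or 10 of 95 on the calendar reading. The first two figures assume last dose on the Week 48 visit day. The number of patients affected cannot be derived from the documents.

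The on-treatment label is the firmer part. Every permitted follow-up visit of a non-rollover completer receives it, so an off-drug finding can be attributed to treatment in the QTcF, vital-sign and weight categories. Early discontinuers are exposed to the windowing problem but, at a 7-day gap, not to this label.

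Efficacy is untouched: follow-up data are not named in the efficacy windowing sentence, and no RWS, dynamometry, Neuro-QoL, PGIC or MRI assessment is scheduled at that visit. This is a minor point, but it concerns a stated rule that gives the wrong result, not a missing detail.

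**What to change.** - **SAP 9.5.1:** delete Safety Follow-up from the safety windowing sentence and report that visit only as its own time point, as 10.3.5 and 10.3.6 already expect. State to which time point a combined early-termination/follow-up visit belongs, since Protocol 4.3.2 allows the two to be merged.
- **SAP 9.3.1.4:** for completers, exclude Safety Follow-up visit assessments from on-treatment in the safety summaries. Leave the status of Week 48 visit assessments as it is, including those split over 2 days.

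Extending the last dose plus 2 days limit to all completers would be too blunt. SAP 3.1 allows up to 5 business days between the parts of a split visit, so valid Week 48 assessments could be lost, and the on-treatment definition also bears on efficacy sensitivity analyses.

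After the change, 0 of the 105 day pairs replace the Week 48 result and 0 follow-up results are labelled on-treatment. By-visit summaries will still hold off-drug values from patients who stopped drug and kept attending, which this edit does not address. The cost is SAP wording and a check that the table shells agree; no data collection changes.

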9.5.2 Methods for handling out-of-window observations

Out-of-window observations will be treated as unscheduled visits. Unscheduled visit data will be excluded from by-visit summaries, but included in the following: efficacy analyses through windowing (see 9.5.1); listings; and in identifying min/max/worst results for laboratory data analyses, etc.

10. STATISTICAL ANALYSES AND METHODOLOGY

10.1 STUDY POPULATION

10.1.1 Disposition of patients

Patient disposition will be summarized for patients screened (pre-randomization disposition) and for the FAS (post randomization disposition). Summaries of patients screened, signed ICF, included/excluded in study will be summarized overall. Patients who received study drug, visits attended, patients' treatment status in the study (completed / discontinued, and reasons for discontinuations), patients' participation status (completed / discontinued and reasons for discontinuation), and who rollover into Part B will be summarized by treatment group and overall.

Screen failures will be summarized by reason for screen failure and presented in a listing.

Patient disposition will be presented in a listing. Patient inclusion/exclusion in the FAS, and safety analysis set will be presented in a listing, by FSHD type.

10.1.2 Protocol deviations

Protocol deviations are classified as Significant or Not Significant, according to a Study Deviation Rules document. Significant protocol deviations will be summarized by deviation type (ICH/GCP, Efficacy, Safety) for all FAS patients, by treatment group. All protocol deviations will be listed, and listings will specify deviation type and whether significant or not significant.

10.1.3 Demographic and baseline characteristics

The following data will be summarized descriptively by treatment group and overall:

- Demographics: Sex, Age in years, Race, Ethnicity
- Height (cm), Weight (kg), BMI (kg/m²)
- Dominant hand
- FSHD Type, Correct FSHD repeat number and category, FSHD repeat number category used for randomization
- [REDACTED]
- FSHD history: Age of first symptoms (years), First symptoms, Age of diagnosis (years), Current pain related to FSHD

Analyses are based on the FAS. All demographic and baseline data will be presented by patient in a listing, by FSHD type and treatment group.

10.1.4 Relevant medical history

Relevant medical history (excluding data collected in the FSHD medical history form) will be MedDRA coded. The number and percentage of patients experiencing relevant medical history prior to enrolling into the study will be summarized by SOC and PT; by treatment group and overall. Analyses are based on the FAS.

All relevant medical history data will be presented by patient in a listing, by FSHD type and treatment group.

10.1.5 Concomitant medications/procedures

Prior and concomitant medications will be summarized by treatment group and overall, for patients in the safety analysis set. Medications are coded using World Health Organization (WHO) drug dictionary (DD) 2021Sep or later and Anatomical Therapeutic Chemical (ATC) Code. Prior and concomitant medications will be summarized by ATC class (level 2) and generic (preferred) name. All prior and concomitant medications and procedures will be presented by patient in a listing, by FSHD type and treatment group.

10.1.6 Treatment exposure and compliance

Exposure and study drug accountability (compliance) will be presented for patients in the Safety Analysis Set.

Study drug exposure

Descriptive statistics will be used to summarize duration of exposure both as a continuous measure in days and weeks and by category: < 8 weeks, \geq 8 weeks, \geq 16 weeks, \geq 24 weeks, \geq 36 weeks, \geq 48 weeks, average daily dose, and cumulative dose.

Study drug accountability

Descriptive statistics will be used to summarize compliance as a continuous measure, and by category: < 80%, 80-120%, \geq 120%. Drug accountability will be presented in a listing, presented by FSHD type, treatment, and patient. For each patient, first dose date, last dose date, and treatment duration will be presented; and at each time-point, for dispensed study drug: bottle number, date and study day tablets were dispensed, and number of tablets dispensed; for returned study drug: date returned, number of tablets returned. The following treatment compliance data will be presented: Number of tablets taken, number of tablets prescribed, duration, and compliance.

10.2 EFFICACY ANALYSES

Efficacy analyses are based on the FAS. The primary and secondary efficacy analyses will also be split by subgroup of the FAS.

10.2.1 Primary efficacy analysis

10.2.1.1 Change from baseline in average total RSA Q1-Q5 with 500 g wrist weight, where average is applied over both arms

For each treatment, descriptive statistics of RWS results (total RSA Q1-Q5) per visit as well as the change from baseline will be presented.

An MMRM will be used to analyze the primary endpoint. The primary analysis of the primary endpoint will be based on the MMRM. See 8.3.1 for analysis methods, where change from baseline in RWS is fitted as the dependent variable for the MMRM. An LME will be also be fitted, where the dependent variable is average total RSA Q1-Q5 with 500g weight, measured at baseline and each post-baseline visit.

Least squares means derived from the MMRM will be plotted over time for both treatment groups with error bars showing standard errors. Annualized percentage changes estimated from the LME will be presented as line charts.

Derived RWS at each time-point, by dominant and non-dominant arm and as an average of both, will be presented by patient in a listing, by FSHD type and treatment group.

10.2.1.2 Other analyses of the primary endpoint

The cumulative distribution plot of change from baseline in average total RSA Q1-Q5 with 500 g wrist weight at Week 48 will be plotted by treatment group. Missing change values are imputed by the worst value per treatment group. Additionally, a bar chart showing the percentage of patients by response categories (e.g., <-0.25, ≥-0.25 to <-0.2, ≥-0.2 to <-0.15, ≥-0.15 to <-0.1, ≥-0.1 to <-0.05, ≥-0.05 to <0, ≥0 to <0.05, ≥0.05 to <0.1, ≥0.1 to <0.15, ≥0.15 to <0.2, ≥0.2 to <0.25, ≥0.25, in percentage points) of change from baseline in average total RSA Q1-Q5 with 500 g wrist weight at Week 48 will be plotted by treatment group. Missing change values are included in the worst category (e.g., change <-0.25). A waterfall plot of change from baseline in average total RSA Q1-Q5 with 500g weight at Week 48 will be plotted, this is a plot of best to worst change from baseline for all subjects with a non-missing change from baseline, by treatment group. A responder plot showing the cumulative percentage of patients by response categories (<-0.25, ≥-0.25, ≥-0.2, ≥-0.15, ≥-0.1, ≥-0.05, ≥0, ≥0.05, ≥0.1, ≥0.15, ≥0.2, and ≥0.25 in percentage points) of change from baseline in average total RSA Q1-Q5 with 500 g wrist weight at Week 48 will be plotted by treatment group. Missing change values are included in the worst category (e.g., change <-0.25).

The relative change from baseline in average total RSA Q1-Q5 with 500 g wrist weight will also be analyzed using the Wilcoxon rank-sum test, stratified by the FSHD repeat number category (see 8.2). The Hodges-Lehmann estimate of the associated treatment difference and asymptotic nonparametric

95% confidence interval as described by Hollander and Wolfe (1999)[5] will be computed. Median relative change from baseline will be plotted by treatment group.

Descriptive statistics will be presented by site.

A binary analysis may be carried out should meaningful score differences (MSDs) be determinable. An MSD is a measure of clinically meaningful within-patient change, which will be explored for change from baseline at 48 weeks in average total RSA Q1-Q5 with 500 g wrist weight, following the draft FDA guidance [6]. This exploration will be conducted by the sponsor's designated vendor. If the MSDs can be determined, for each treatment group, the number and percentage of patients at or above an MSD and the number and percentage of patients below the MSD will be presented. A patient with a missing change from baseline in average total RSA Q1-Q5 with 500 g wrist weight will be considered as below the MSD. The proportion of patients at or above MSDs at Week 48 will be compared between treatment groups using the Cochran-Mantel-Haenszel test stratified by FSHD repeat number category, and a two-sided p-value will be presented. Similar analysis will be performed using the lower bounds of MSDs as cut-off points as well as 0 as a cut-off point.

In addition, the analysis described in 10.2.1.1 will be repeated for the following:

- (1) Sensitivity analyses (see below)
- (2) For certain subgroups (listed in Section 8.5)

Sensitivity Analysis 1: MMRM with on-treatment measurements only

This sensitivity analysis of the primary endpoint will be similar to that used for the primary analysis of the primary endpoint. The key difference is that, for patients who prematurely discontinue study treatment, this MMRM will include only the measurements up to 2 days (inclusive) after the last dose of study drug.

Sensitivity Analyses 2, 3 and 4: MMRM with missing data imputed

In the primary analysis of the primary endpoint, missing data are assumed to be missing at random. To minimize the amount of missing data, patients who prematurely discontinue study treatment will be encouraged to remain in the study and continue with all remaining scheduled study visits for efficacy assessments.

To assess the impact of missing data and the assumption that data are missing at random, 3 multiple imputation (MI) algorithms will be applied if 10% or more of the patients have missing changes from baseline in average total RSA Q1-Q5 with 500 g wrist weight at Week 48 in either treatment group. A missing change from baseline in average total RSA Q1-Q5 with 500 g wrist weight will be imputed starting from the first visit with a missing change value, for which every change value at every subsequent visit through Week 48 is also missing. For intermediate missing data, i.e., missing change values that fall between two non-missing ones, it is reasonable to assume that they are missing at random and therefore will not be imputed.

If a patient discontinues the study because of death, the patient's missing values of average total RSA Q1-Q5 with 500 g wrist weight after the last non-missing value will be imputed as 0, the lowest possible value of average total RSA Q1-Q5 with 500 g wrist weight. It will be used to derive changes from baseline.

Other missing values after the last non-missing value will be classified as missing category 1 or missing category 2 as follows:

- Missing category 1: A patient discontinues the study because of adverse events, noncompliance, or investigator discretion, or because a patient requires a prohibited medication.
- Missing category 2: A patient discontinues the study for other reasons or completes the study but has missing value(s) at the last or last several visits.

Sensitivity Analysis 2: MMRM with discontinuation reason-based MI

For missing values in missing category 1: The missing changes from baseline after the last non-missing change value will be imputed as random values drawn from a normal distribution with mean equal to the 25th percentile of the non-missing changes from baseline at the given visit and with variance estimated using the non-missing changes at that visit from the same treatment group.

For missing values in missing category 2: The missing changes from baseline after the last non-missing change value will be imputed as random values drawn from a normal distribution with mean equal to the mean of the non-missing changes from baseline at the given visit and with variance estimated using the non-missing changes at that visit from the same treatment group.

This process will be repeated 20 times to form 20 imputed datasets. The same MMRM model as is used for the primary endpoint analysis will be applied to each imputed dataset to estimate mean change from baseline for each treatment group, and the difference between treatment groups in mean change from baseline at Week 48. These 20 model results will be combined using the SAS procedure MIANALYZE to obtain MI estimates with SE, 2-sided 95% CI, and 2-sided p-value.

Sensitivity Analysis 3: MMRM with placebo-based MI

For missing values in missing category 1: The missing changes from baseline after the last non-missing change value will be imputed as random values drawn from a normal distribution with mean equal to the mean of the non-missing placebo group changes from baseline at the given visit and with variance estimated using the non-missing changes at that visit from the placebo group.

For missing values in missing category 2: The missing changes from baseline after the last non-missing change value will be imputed as random values drawn from a normal distribution with mean equal to the mean of the non-missing changes from baseline at the given visit and with variance estimated using the non-missing changes at that visit from the same treatment group.

This process will be repeated 20 times to form 20 imputed datasets. The same MMRM model as is used for the primary endpoint analysis will be applied to each imputed dataset to estimate mean change from baseline for each treatment group, and the difference between treatment groups in

mean change from baseline at Week 48. These 20 model results will be combined using the SAS procedure MIANALYZE to obtain MI estimates with SE, 2-sided 95% CI, and 2-sided p-value.

[Sensitivity Analysis 4: MMRM with tipping point MI](#)

The missing changes from baseline after the last non-missing change value will be imputed as random values drawn from a normal distribution with mean equal to the mean of the non-missing changes from baseline at the given visit and with variance estimated using the non-missing changes at that visit from the same treatment group.

For missing values in missing category 1 of patients in the losmapimod group, a delta that is equal to m times the difference in LS means between treatment groups (Losmapimod 15 mg BID – Placebo BID) at the given visit obtained from the primary MMRM analysis will be subtracted from their imputed values, with m starting from 0%, 10%, 20%, .., and up to 100% or higher, until conclusion from the primary MMRM analysis is overturned, or it becomes clinically meaningless to go even higher.

For each m , this process will be repeated 20 times to form 20 imputed datasets. The same MMRM model as is used for the primary endpoint analysis will be applied to each imputed dataset to estimate mean change from baseline for each treatment group, and the difference between treatment groups in mean change from baseline at Week 48. These 20 model results will be combined using the SAS procedure MIANALYZE to obtain MI estimates with SE, 2-sided 95% CI, and 2-sided p-value. Complete the tipping point MI analysis with different m 's as described in the above paragraph.

In applying the above-mentioned 3 MI algorithms, missing changes from baseline in average total RSA Q1-Q5 with 500 g wrist weight will be imputed from normal distributions. The underlying normality assumption of changes from baseline will be checked using a normal probability plot, p-value from the Shapiro-Wilk test, and skewness and kurtosis of non-missing changes at Week 48 for each treatment group. The homogeneity of variances will be checked using the Levene test and Brown-Forsythe test on non-missing changes at Week 48. In case the change data significantly deviate from the normality assumption, they will be fitted against a distribution, and missing changes will be sampled from the fitted distribution.

[Sensitivity analysis 5: Nonparametric rank repeated measures analysis of covariance \(ANCOVA\)](#)

This sensitivity analysis of the primary endpoint will evaluate the robustness of the primary analysis of the primary endpoint against model assumptions of normal residuals and linear relationship between the response and covariates. The rank two-way repeated measures ANCOVA will be applied upon rank transformed response and rank transformed covariates. Here, the response is change from baseline in average total RSA Q1-Q5 with 500 g wrist weight, the two factors are treatment group and visit, and the covariates are baseline value of average total RSA Q1-Q5 with 500 g wrist weight, baseline value by visit interaction, stratification category, and region. Ranks are applied at each visit within the FAS, not within each treatment group. The generalized estimating equation technique will be employed to construct rank tests [7].

Sensitivity Analysis 6: MMRM adjusting for correct FSHD repeat number category

This sensitivity analysis of the primary endpoint will be similar to that used for the primary analysis of the primary endpoint. The key difference is that, for patients with stratification category used at randomization being different from the correct category, this MMRM will adjust for the correct category.

